5.4 Non Randomisation

Participating clinicians/research nurses will be asked to complete a log of all patients screened for eligibility who are not randomised either because they are ineligible or because they decline participation. Anonymised information will be collected including:

- the reason not eligible for trial participation or
- eligible but declined
- age
- gender
- ethnicity

6. TREATMENT DETAILS

6.1 Routine pre-treatment tests

- On day 1 of each drug therapy cycle (= the day of irinotecan administration), or within five days prior, patients should undergo the following:
 - Medical history and physical examination, including assessment of WHO performance status
 - FBC, U&Es, magnesium, calcium and LFTs
 - If WBC < $3.0 \times 10^9/l$; neutrophils < $1.5 \times 10^9/l$, plts < $100 \times 10^9/l$; bilirubin > 1.5 ULN or estimated GFR < 50 ml/min, see section 6.4 for advice
- NB patients on **IrCs** may start their ciclosporin the day before these tests, but see note in section 6.4 if a treatment is delayed

NB if the patient is on a treatment break from irinotecan, panitumumab should be administered at 9mg/kg every three weeks (see section 6.2.5). When panitumumab is administered as a monotherapy the pre-treatment tests should be as detailed above.

6.2 Drug administration

Patients will receive treatment, once every three weeks, according to their randomisation allocation as follows:

- **Ir** (Control):
 - Irinotecan 350 mg/m² i.v. infusion (over 90* minutes)
(Irinotecan 300 mg/m² if age >70 years or PS=2)
- **IrCs**:
 - Irinotecan 140 mg/m² i.v. infusion (over 40* minutes)
(Irinotecan 120 mg/m² if age >70 years or PS=2)
PLUS
 - Ciclosporin** 3mg/kg t.d.s. by mouth for 3 days starting in the morning the day before the dose of Irinotecan
- **IrPan**:
 - Panitumumab 9 mg/kg i.v. infusion (over 60* minutes), then
 - Irinotecan 350 mg/m² i.v. infusion (over 90* minutes),
(Irinotecan 300 mg/m² if age >70 years or PS=2)

Please note that there is no requirement for a break between the Pan and Ir Infusions. If a patient's weight changes by > 10% from baseline the doses of all drugs should be re-calculated.

* Irinotecan and panitumumab infusion times may be reduced if well tolerated; see sections 6.2.2 and 6.2.4 respectively

** see section 6.2.3

Please note that any diluent used in this study must be an EU marketed product.

Dose capping

All dosing is to be determined solely by patient body surface area as calculated from actual body weight. Doses should not be capped.

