[name], Consultant Surgeon, University of Birmingham, Clinical Research Block, Queen Elizabeth Hospital, [name]

[name], Professor of Surgery, Department of Surgery, [name], University Hospital Nottingham, [name].

[name], Reader in Medical Statistics & Epidemiology, MRC Clinical Trials Unit, Cancer Group, [name].

PICCOLO Flow Diagram

* Formalin-fixed paraffin-embedded blocks from primary and/or metastatic tumour. See section 5.1

** The lower dose of irinotecan is for patients aged ≥70 years, or of any age if WHO performance status 2. If the lower dose is well tolerated for the first two cycles it may be escalated to the full dose thereafter.

GLOSSARY OF TERMS

AE	Adverse Event
AUC	Area under the plasma concentration-versus-time curve
CR	Complete Response
CRF	Case Report Form
Cs	Ciclosporin
CTA	Clinical Trials Authorisation
CTC	Common Toxicity Criteria
CTRU	Clinical Trials Research Unit
DMEC	Data Monitoring and Ethics Committee
DLQI	Dermatology Life Quality Index
EGFr	Epidermal Growth Factor Receptor
EQ-5D	EuroQol Questionnaire
GCP	Good Clinical Practice
Ir	Irinotecan
IrCs	Irinotecan plus ciclosporin
IrPan	Irinotecan plus panitumumab
LFTs	Liver Function Tests
LREC	Local Research Ethics Committee
MHRA	Medicine and Healthcare Products Regulatory Agency
NCI	National Cancer Institute
NICE	National Institute of Health and Clinical Effectiveness
OS	Overall Survival
PA	Patient Acceptability
Pan	Panitumumab
PD	Progressive Disease
PFS	Progression-free Survival
PK	Pharmacokinetics
PR	Partial Response
QL	Quality of Life
EORTC QLQ-C30	European Organisation for Research & Treatment of Cancer questionnaire
REC	Research Ethics Committee
SAE	Serious Adverse Event
SD	Stable disease
SNP	Single Nucleotide Polymorphism
SUSARs	Suspected Unexpected Serious Adverse Reactions
U&Es	Urea & Electrolytes
VEGF	Vascular Endothelial Growth Factor
WBC	White Blood Cells
WHO	World Health Organisation

CONTENTS

TITLE PAGE	
SIGNATURES PAGE	
KEY CONTACTS	
PICCOLO FLOW DIAGRAM	
GLOSSARY OF TERMS	
1. BACKGROUND	10
2. AIMS AND OBJECTIVES	16
3. TRIAL DESIGN	17
4. ELIGIBILITY	18
PATIENT SELECTION	18
5. REGISTRATION AND RANDOMISATION	20
5.1 REGISTRATION	20
5.2 RANDOMISATION	21
5.2.1 Recruitment for Pharmacokinetics (PK) Sub-study	22
5.3 BASELINE AND REASSESSMENT CT SCAN	23
5.4 NON RANDOMISATION	23
6. TREATMENT DETAILS	24
6.1 ROUTINE PRE-TREATMENT TESTS	24
6.2 DRUG ADMINISTRATION	24
6.2.1 Routine antiemetics, etc	25

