- Patient's 5 digit trial no assigned at registration
- authorisation code and PIN
- basic patient details including initials, date of birth, hospital number, weight
- name of centre and centre code
- name of consultant and person making randomisation
- confirmation of eligibility (including date of written informed consent)

NB. The patient should be asked to complete the baseline quality of life questionnaire prior to randomisation.

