6.3 Treatment Duration & Treatment Breaks

- The initial treatment period is 12 weeks followed by clinical and radiological re-assessment
- Patients with clinical benefit (radiological and symptomatic response or stabilisation) will be offered further treatment until disease progression or toxicity

- After the initial 12 weeks patients with stable or responding disease may have a planned treatment break of up to 6 weeks (i.e. omit up to 2 cycles of treatment, re-starting up to 9 weeks after the last irinotecan dose). In this event please note:
 - a) there is no change in the scanning schedule i.e. patients should be scanned at 24, 36, 48 weeks etc post randomisation until progression
 - b) patients on IrPan should continue to receive Pan as a single agent during the treatment break (see section 6.2.5)
 - c) If clinical or radiological progression emerges during a break, the patient should resume their allocated treatment, provided that the treating consultant considers this to be in the patient's best interest. Patients on the IrPan arm who have received single-agent Pan during the break should re-start IrPan.

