Appendix 4. Pharmacokinetics (PK) Sub-study

The regimen of IrCs used in this trial has been chosen, based on PK data from previous studies, to generate the same systemic exposure to irinotecan and its active metabolite SN38 (measured as AUC – the area under their plasma concentration/time curves) as standard single-agent irinotecan. In order to confirm whether this is in fact achieved, 20 patients in the IrCs arm are being invited to participate in the PK Sub-study.

Any centre with facilities and experience in PK may register for the PK Sub-study. In those centres, all patients randomised to the IrCs arm will then be invited to participate in the PK Sub-study; patients are however free to decline participation without affecting any other aspect of their trial participation or medical care. Recruitment to the PK Sub-study will be discontinued when the required target of 20 patients have completed two PK study days.

PK Sub-study entry procedure

- Patients will be asked to sign the PK Sub-study Consent Form
- Two consecutive treatment cycles during the first four will be nominated as 'PK Sub-study cycles'. These will normally be cycles 1 & 2, however the PK Sub-study may be deferred to cycles 2 & 3, or cycles 3 & 4, if these are more convenient for the patient and Centre.
- The centre will complete the PK Sub-study Registration Form and telephone the CTRU on [name] to obtain the randomised allocation i.e. **allocation to receive, in random order, one of these two cycles as IrCs and one as standard single-agent irinotecan.**
- Patients planned to receive Ir at the lower dose because of age ≥ 70 or PS=2 (see section 6.2) may still take part in the PK Sub-study. In this case the lower dose will be used for both the IrCs study cycle (120 mg/m²) and the standard Ir study cycle (300 mg/m²).
- Any patient requiring irinotecan dose reduction for toxicity before completion of the two PK study cycles will be removed from the PK Sub-study.

PK Sub-study Sampling Procedure

- The patient will need to have blood samples taken 6, 24 and 48 hours after the end of irinotecan infusion. For this reason, on PK study days we recommend that the patient is booked to attend in time for administration of irinotecan early (e.g. 10 am) to avoid late evening sampling.
- For the IrCs cycle we recommend you telephone the patient 2 days before to remind them to start their Cs at 8 am the day before attending for irinotecan.

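### Minor: the age cut-off for the lower irinotecan dose is >70 in section 6.2 but ≥70 in the flow diagram note and Appendix 4

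*Protocol*

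**What the plan says.** Protocol section 6.2 (Drug administration) gives each arm a full irinotecan dose followed by a lower dose in brackets. For Ir and for IrPan the full dose is 350 mg/m² and the bracket reads "Irinotecan 300 mg/m² if age >70 years or PS=2". For IrCs the full dose is 140 mg/m² and the bracket reads "Irinotecan 120 mg/m² if age >70 years or PS=2". The cut-off >70 therefore appears three times, once per arm.

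The note under the flow diagram states the rule differently: "The lower dose of irinotecan is for patients aged ≥70 years, or of any age if WHO performance status 2". It then adds an allowance that section 6.2 does not repeat: "If the lower dose is well tolerated for the first two cycles it may be escalated to the full dose thereafter".

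Appendix 4 (PK Sub-study) also includes age 70 and names section 6.2 as the place where the rule is set: "Patients planned to receive Ir at the lower dose because of age ≥ 70 or PS=2 (see section 6.2").

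The three places agree on performance status 2. The lower dose levels in section 6.2 and Appendix 4 also agree (300 and 120 mg/m²). Only the treatment of age 70 differs.

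**The concern.** This is a prescribing threshold for a cytotoxic drug, and the current text gives two versions of it. Section 6.2 is where a prescriber or pharmacist would naturally look, and it carries the less cautious version. Appendix 4 attributes to section 6.2 a cut-off that section 6.2 does not print, so the two cannot both state the intended rule. Nothing in the protocol says which text takes precedence.

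Two sites, or two people at one site, could therefore start the same 70-year-old on different doses while each believes the protocol has been followed. The Background (section 1) describes irinotecan diarrhoea as potentially life-threatening when it coincides with myelosuppression. A clear boundary for the reduced dose is therefore worth having, even though few patients are likely to sit on it.

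**Working it through.** There is no planned figure to reproduce. The check sets the texts side by side and then works out the dose consequence.

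**Cut-offs as printed**

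| Place in Protocol | Age condition | Other condition |
|---|---|---|
| Section 6.2, Ir, IrCs and IrPan lines | >70 | PS 2 |
| Flow diagram note | ≥70 | PS 2 at any age |
| Appendix 4, citing section 6.2 | ≥70 | PS 2 |

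**Who is affected.** Performance status 2 triggers the lower dose in all three places, so those patients are unaffected. With age in completed years, patients of 69 or younger and 71 or older are classified alike by both wordings. What remains is age 70 with performance status 0 or 1.

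**Difference per cycle** (doses from section 6.2)

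- Ir and IrPan: (350 − 300) / 350 = 50 / 350 = 14.3%
- IrCs: (140 − 120) / 140 = 20 / 140 = 14.3%

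The two agree because the IrCs dose is 40% of standard at both levels: 140 / 350 = 120 / 300 = 0.40.

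**Difference over the initial treatment period.** Section 6.3 sets its length: "The initial treatment period is 12 weeks followed by clinical and radiological re-assessment". Treatment is given every three weeks (section 6.2), so this is 12 / 3 = 4 cycles. The totals below assume that all four are given, with no delay and no toxicity reduction.

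| Schedule | Ir, IrPan (mg/m²) | IrCs (mg/m²) |
|---|---|---|
| Full dose throughout | 4 × 350 = 1400 | 4 × 140 = 560 |
| Lower dose, escalated from cycle 3 | 2 × 300 + 2 × 350 = 1300 | 2 × 120 + 2 × 140 = 520 |
| Lower dose throughout | 4 × 300 = 1200 | 4 × 120 = 480 |

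- With escalation: 100 / 1400 = 40 / 560 = 7.1% below full dose.
- Without escalation: 200 / 1400 = 80 / 560 = 14.3% below full dose.

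**Reach into the statistics.** Age is not among the minimisation factors listed in section 5.2, and the cut-off enters no endpoint, sample size calculation or analysis in sections 10 to 12. It reads the same in each arm, so it favours none. The number of patients aged 70 with performance status 0 or 1 cannot be derived from the protocol.

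**The case against.** Four points can be made in the plan's defence.

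1. **The symbol may be a reading error.** A ≥ printed as an underlined > could have lost its line when the PDF was converted. Appendix 4 points to section 6.2 for ≥70, which fits that explanation. The three dose lines probably share one typography, so they are not three independent confirmations. On the other side, ≥ survives in many other places, including sections 4 and 6.4. The possibility stands and calls for a check of the source, but it is not shown.

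2. **The gap depends on how age is read.** If >70 means any time past the 70th birthday, the two wordings almost coincide. Exact age is available, because randomisation requires "basic patient details including initials, date of birth, hospital number, weight". This narrows the point. It does not remove it, because section 6.2 does not say how age is to be counted and completed years is the ordinary clinical reading.

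3. **The intended rule can be inferred.** Two of the three places agree, and one of them refers to the third. That helps a reader who compares all three, but not someone prescribing from section 6.2 alone.

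4. **The consequence is small.** Both doses are protocol doses, and the lower one may be raised after two well-tolerated cycles. Section 6.4 prescribes larger changes for toxicity (20% in many cases, 50% for certain liver abnormalities), and section 6.10 leaves changes of regimen to the clinician. The PK Sub-study is protected because Appendix 4 applies the lower dose level to both PK cycles of the same patient. All of this is correct, and it is why the point is graded minor.

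**Conclusion.** The inconsistency is real in the text as supplied and is a minor fault. For patients aged 70 with performance status 0 or 1, the starting dose is undetermined by 14.3% per cycle. Over four uninterrupted cycles that becomes 7.1% with escalation from cycle 3, or 14.3% without it. This rests on two assumptions: that age is counted in completed years, and that section 6.2 really prints >. Confidence is therefore medium until the source file is checked.

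No treatment comparison, power figure or error rate is affected. The cumulative totals describe what one patient might receive and are not evidence of harm or bias.

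**What to change.** First look at the source PDF to see whether section 6.2 prints > or ≥. If it prints ≥, nothing needs changing. If it prints >, replace it with ≥ in the three dose lines of section 6.2. That matches the flow diagram note and Appendix 4, and it gives the more cautious of the two doses.

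Then send sites a short clarification. The cost is one symbol in three lines plus that notice. Nothing in the design or the analysis needs to change.

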6.2.1 Routine antiemetics, etc

In all three treatment arms:

- Immediately prior to irinotecan infusion:
 - dexamethasone 8mg i.v. + granisetron 3 mg i.v. or equivalents
- If cholinergic symptoms occur during/after irinotecan infusion:
 - atropine 0.3 mg s/c stat, and thereafter prophylactically for future cycles
- Following irinotecan infusion:
 - dexamethasone 4 mg orally, t.d.s. x 1 day; b.d. x 1 day and o.d. x 1 day
- Take-home medications to be prescribed routinely:
 - domperidone 10 mg t.d.s. p.r.n. for up to 7 days (please avoid metoclopramide as it may interact with Cs)
 - ensure patient has supplies of loperamide, and ciprofloxacin to use as required for diarrhoea, and instructions for their use (see section 6.4)
 - For patients on IrCs, the next cycle's prescription of ciclosporin should be issued

It is acceptable for centres to administer a variant of the above antiemetic schedule, as per local policy, but this should be applied to all three treatment arms.

6.2.2 Irinotecan infusion time

If treatment is tolerated without major acute cholinergic side-effects, the irinotecan infusion time may be reduced to 30 minutes (**Ir or IrPan**) or 15 minutes (**IrCs**) for subsequent cycles.

6.2.3 Ciclosporin administration

For patients receiving **IrCs**, the ciclosporin doses should be the same throughout the day and be spaced out as well as possible (e.g. 8am, 3pm and 10pm). See appendix 5 for details of ciclosporin dosing. The time of the irinotecan may fall close to the second ciclosporin dose on the second day, but the exact timing is not critical. Patients taking ciclosporin will be given a diary to record the time and number of doses taken.

Ciclosporin may be given as Neoral™ soft gelatin capsules or Neoral™ oral solution (Novartis) as preferred by the patient.

CAUTION: It is important to ensure that patients who have been taking ciclosporin at home are not accidentally given irinotecan at the full single-agent Ir dose. Each centre must ensure that appropriate checks are in place in medical, nursing and pharmacy systems to guard against this.

Prior to receiving irinotecan, patients should have taken 4-5 doses of ciclosporin (3 the previous day and 1 or 2 on the day of irinotecan, depending on the time of day the infusion is given). If the patient has taken at least 3 of the planned ciclosporin doses the irinotecan infusion may be given. The patient should be encouraged to take future ciclosporin doses as prescribed. If the patient has taken ≤ 2 doses of ciclosporin the irinotecan infusion should NOT be given. Ciclosporin should be re-prescribed and the irinotecan infusion re-scheduled for the earliest feasible opportunity (e.g. 2 days later).

6.2.4 Panitumumab administration

The dose of 9 mg/kg is calculated using actual body weight (the weight at baseline may be used throughout unless this changes by $> 10\%$ during the study) and is diluted in a minimum of 100 ml of pyrogen-free 0.9% sodium chloride solution. The final concentration should not exceed 10 mg/mL, therefore for patients weighing > 110 kg an infusion volume of > 100 mL is required.

Panitumumab is administered IV by an infusion pump through a peripheral line or indwelling catheter **using a 0.22-micron in-line filter infusion set-up** over approximately 60 minutes. If well tolerated subsequent infusions can be reduced to 30 minutes but the infusion rate must not exceed 20 mg/min. In the unlikely event a subject's actual weight requires greater than 150ml volume infusion, panitumumab must be administered over approximately 90 minutes. Strict adherence to aseptic technique will be used during panitumumab preparation and administration. The bag should be labelled per site pharmacy/ward Standard Operating Procedures (SOPs) and promptly forwarded to the chemotherapy unit for infusion. Once diluted, panitumumab should be used within 6 hours if stored at room temperature or within 24 hours if refrigerated at 2-8°C.

There is no observation period for panitumumab.

6.2.5 Administration of panitumumab during chemotherapy breaks or delays

In the event that chemotherapy is to be delayed (e.g. for toxicity), panitumumab will be administered at a dose of 2.5 mg/kg on a weekly schedule until the beginning of the next chemotherapy cycle, when the standard schedule will be resumed.

For patients having a planned chemotherapy break (e.g. after cycle 4, in responding or stable patients) panitumumab will be administered as a single agent, at 9 mg/kg every 3 weeks, during the break.

6.3 Treatment Duration & Treatment Breaks

- The initial treatment period is 12 weeks followed by clinical and radiological re-assessment
- Patients with clinical benefit (radiological and symptomatic response or stabilisation) will be offered further treatment until disease progression or toxicity

- After the initial 12 weeks patients with stable or responding disease may have a planned treatment break of up to 6 weeks (i.e. omit up to 2 cycles of treatment, re-starting up to 9 weeks after the last irinotecan dose). In this event please note:
 - a) there is no change in the scanning schedule i.e. patients should be scanned at 24, 36, 48 weeks etc post randomisation until progression
 - b) patients on IrPan should continue to receive Pan as a single agent during the treatment break (see section 6.2.5)
 - c) If clinical or radiological progression emerges during a break, the patient should resume their allocated treatment, provided that the treating consultant considers this to be in the patient's best interest. Patients on the IrPan arm who have received single-agent Pan during the break should re-start IrPan.

6.4 Management of Toxicity – Delays and Dose-reductions

General Rules:

- Except where specified below, non-haematological toxicity which persists at grade ≥ 2 when the next treatment is due requires a delay of one week.
- Except where specified below, if any non-haematological toxicity reaches grade ≥ 3 , all subsequent treatment is given at a 20% reduced dose.
- For patients on IrPan who require a dose delay due to irinotecan toxicity, Pan is continued once-weekly (2.5mg/kg) until the Ir is resumed.
- For patients on Ircs who require a delay due to irinotecan toxicity, Cs is stopped, and a new full 3-day course started the day before Ir is resumed.

Management of specific toxicities:

- Acute cholinergic syndrome
 - Irinotecan may provoke acute cholinergic syndrome (diarrhoea, sweating, salivation, bradycardia, etc). This may start during the drug infusion or shortly after.
 - Treatment for cholinergic syndrome is atropine sulphate 0.3 mg s/c. This may be given according to local policy.
- Haematological toxicity
 - Check FBC before each cycle. Delay 1 week if WBC $< 3.0 \times 10^9/l$, neutrophils $< 1.5 \times 10^9/l$ or platelets $< 100 \times 10^9/l$. Only treat when FBC is above these limits.
 - If a delay of two consecutive cycles or 1 delay of ≥ 2 weeks occurs, reduce the irinotecan dose by 20% and continue at the lower dose for subsequent cycles unless further toxicity occurs
 - If a further delay(s) for myelotoxicity occurs despite a 20% dose reduction, a further dose reduction may be made, at the discretion of the treating clinician
 - In the event of febrile neutropenia reduce the irinotecan dose by 20% for all subsequent cycles
- Diarrhoea
 - Irinotecan delayed diarrhoea may, if untreated, become severe. Early intervention with high-dose loperamide is important.
 - Patients should be carefully instructed about this side effect, given a written information sheet, telephone contact numbers and supplies of loperamide and ciprofloxacin as per local practice. Care should be taken that out-of-hours staff answering patient queries are familiar with the protocol.

- Patients should start loperamide at the first loose stool: 4 mg, then 2 mg every 2 hours until 12 hours after the last loose stool (up to a maximum of 48 hours)
- If diarrhoea lasts > 24 hours, ciprofloxacin 500 mg bd should be added. If it lasts > 48 hours, or if the patient reports symptoms of dehydration, he/she should be admitted acutely for rehydration and further management (e.g. octreotide).
- After an episode of severe diarrhoea (e.g. requiring admission), delay until full recovery then resume at 20% reduced dose irinotecan for all subsequent cycles
- If diarrhoea from the previous cycle has not resolved by the time the next cycle is due, delay 1 week
- Hepatobiliary function
 - LFTs should be checked before each treatment cycle. Patients with serum ALP >5 x ULN or serum bilirubin in the range 1.5-3 x ULN require a 50% dose reduction of irinotecan. If the LFTs subsequently improve to below these limits, full-dose treatment may be resumed
 - Patients with serum bilirubin >3 x ULN should not receive irinotecan. If bilirubin subsequently falls, treatment may be resumed as above.
- Renal function
 - At the time of trial entry renal function must satisfy entry criteria. Subsequently re-check serum creatinine at each cycle. The patient should not receive treatment if estimated GFR falls below 30 ml/min.
- Hypomagnesemia Management
 - Plasma magnesium should be checked prior to each cycle. If below 0.7 mmol/l, start oral magnesium supplements (initially, we recommend oral Magnaspartate® [KoRa Healthcare], one 10mmol sachet t.d.s.). Serum magnesium should be maintained above 0.4 mmol/l at all times.
- Panitumumab dermatological toxicity
 - Over 90% of patients treated with panitumumab in previous trials developed skin or nail side-effects, usually a mild-to-moderate acneiform rash, similar to that seen during cetuximab therapy. This reached NCI CTC Grade 3 in 7% and resulted in discontinuation of the drug in 1% of patients.
 - All patients allocated to receive panitumumab should be forewarned that they are very likely to develop a rash. At the first development of a rash we recommend:
 - start an oral tetracycline, e.g lymecycline 408 mg b.d.
 - start topical emollients (e.g. E45®) and bath additives (e.g. Hydromol®).
 - Skin toxicities will be recorded as adverse events on the Treatment Case Report Form and will be graded using a modified version of NCI CTC version 3.0, as detailed in Appendix 2.

The following guidelines should be used for adjusting panitumumab in the event of skin or nail toxicity:

- If severe skin or nail toxicity occurs, the next panitumumab dose should be withheld and Ir administered alone. Examples of reasons for withholding a planned dose of panitumumab include:
 - Symptomatic skin- or nail-related toxicity requiring strong analgesia, systemic steroids, or felt to be intolerable by the patient

- Skin or nail infection requiring IV antibiotics or IV antifungals
- Need for surgical debridement
- Any skin- or nail-related serious adverse event
- After withholding a dose, panitumumab may be reintroduced at the next treatment cycle, at 75% of the original dose, provided:
 - the adverse event has improved to \leq Grade 2,
 - the subject has recovered to the point where symptomatic skin or nail-related toxicity is no longer felt to be intolerable,
 - systemic steroids or strong analgesics are no longer required,
 - in the case of skin or nail infection, IV antibiotic or IV antifungal treatment is no longer required
- If the 75% dose reduction is tolerated, at the next cycle the panitumumab dose may be escalated to the original dose.
- If, after stopping and resuming panitumumab, a **second** withdrawal is required, any further reintroduction should be at 50% dose. If the 50% dose is tolerated, at the next cycle the panitumumab may be escalated to 75% of the original dose but should not be re-escalated to full dose.
- If, after stopping and resuming panitumumab, a **third** withdrawal is required the patient should be discontinued from receiving panitumumab
- If after withholding a dose of panitumumab, by the next treatment cycle:
 - the adverse event has NOT improved to Grade 2
 - the subject has NOT recovered to the point where symptomatic skin- or nail-related toxicity is no longer felt to be intolerable
 - systemic steroids or strong analgesics are still required
 - or, in the case of skin or nail infection, IV antibiotic or IV antifungal treatment is still required...the patient should be discontinued from receiving panitumumab.
- Panitumumab non-dermatological toxicity
 - In single-agent panitumumab studies, grade 1-2 diarrhoea, nausea, vomiting, abdominal pain and fatigue have been reported. It is therefore possible that panitumumab may contribute to these toxicities when given in combination with irinotecan.
 - Toxicities will be recorded as adverse events on the Treatment Case Report Form (see section 8.2)
